4.2. Scientific rationale for study design

In China, under the NIP, a 3-dose primary vaccination against poliovirus is currently recommended during the first year of life in a 2, 3 and 4 months of age schedule. *Rotarix* should be given in a 2-dose schedule between 6-24 weeks of age with an interval of at least 4 weeks between doses. Till date, there is no data available on the immunogenicity and safety of IPV when co-administered with *Rotarix* PCV-free, in healthy Chinese infants.

The current study is therefore designed to assess the immunogenicity and safety of IPV when it is co-administered with *Rotarix* PCV-free, compared to administration of the vaccines separately. There are 2 parallel arms:

- **Co-administration group:** participants will receive *Rotarix* PCV-free co-administered with IPV at Month 0.5 and Month 1.5, and IPV at Month 2.5.
- **Staggered group:** participants will receive *Rotarix* PCV-free at Day 1 and Month 1, and IPV at Month 0.5, Month 1.5, and Month 2.5.

The study will enroll infants 6-10 weeks of age. This will ensure compliance with the recommendations mentioned below, including for participants of the Co-administration group who will receive the first dose of *Rotarix* and IPV at 2 weeks after enrolment:

- As per CDC recommendation, the first dose of *Rotarix* should be given before an infant is 15 weeks of age and the second dose before they turn 8 months old.
- As per EU SmPC recommendation, the first dose of *Rotarix* may be administered from 6 weeks of age. There should be an interval of at least 4 weeks between doses. The second dose should preferably be given before 16 weeks of age but must be completed by the age of 24 weeks.
- In China, IPV is recommended as 2 doses at the age of 2 and 3 months and no later than 13 weeks of age for the first dose.

Please refer to the IB for further information on *Rotarix*.

Please refer to the PI for further information on Beijing Biological Products Institute Co.,Ltd. IPV.

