● is used to indicate a study procedure that requires documentation in the individual eCRF.

○ is used to indicate a study procedure that does not require documentation in the individual eCRF.

^a immunosuppressive or immunodeficient conditions.

Note: Details of COVID-19 infection-related signs and symptoms should also be recorded in a separate eCRF page.

*Number of days for recording of solicited events after each dose of study intervention is defined by Chinese authorities [NMPA, 2019a].

Table 3 Intervals between study visits for Co-administration group

Interval	Optimal interval	Allowed interval range	Allowed interval during special circumstances [#]
Visit 1→Visit 2	15 days	14-18 days between study enrolment and Dose 1 of IPV and Rotarix PCV-free	14-45 days
Visit 2→Visit 4	30 days	28-36 [†] days between Dose 1 of IPV and Rotarix PCV-free and Dose 2 of IPV and Rotarix PCV-free	28-60 days
Visit 4→Visit 6	30 days	28-36 [†] days between Dose 2 of IPV and Rotarix PCV-free and Dose 3 of IPV and BS for assessment of Rotavirus Ab, IgA	28-60 days
Visit 6→Visit 7	30 days	30-36 [†] days between Dose 3 of IPV and BS for assessment of anti-poliovirus types 1, 2 and 3 Ab	30-60 days

Ab: Antibody; BS: Blood sampling; IgA: Immunoglobulin A; IPV: Inactivated poliovirus vaccine; PCV: Porcine circovirus; PCV-free: no detection of PCV-1 and PCV-2 according to the limit of detection of the tests used

[†] Participants will not be eligible for inclusion in the Per Protocol Set for immunogenicity if they make the study visit outside this interval. Interval is computed as the difference between the 2 dates of the study procedure.

[#] Refer to Section 8 for more details on special circumstances (e.g., COVID-19 pandemic).

Table 4 Intervals between study visits for Staggered group

Interval	Optimal interval	Allowed interval range	Allowed interval during special circumstances [#]
Visit 1→Visit 2	15 days	14-18 [†] days between Dose 1 of Rotarix PCV-free and Dose 1 of IPV	14-45 days
Visit 1→Visit 3	30 days	28-36 [†] days between Dose 1 and Dose 2 of Rotarix PCV-free	28-60 days
Visit 2→Visit 4	30 days	28-36 [†] days between Dose 1 and Dose 2 of IPV	28-60 days
Visit 3→Visit 5	30 days	28-36 [†] days between Dose 2 of Rotarix PCV-free and BS for assessment of Rotavirus Ab, IgA	28-60 days
Visit 4→Visit 6	30 days	28-36 [†] days between Dose 2 and Dose 3 of IPV	28-60 days

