5.1. Inclusion criteria

All participants must satisfy ALL the following criteria at study entry:

- Participants' parent(s)/Legally Acceptable Representative(s) (LAR), who, in the opinion of the investigator, can and will comply with the requirements of the protocol.
- Written or witnessed/thumb printed informed consent obtained from the parent(s)/LAR(s) of the participant prior to performance of any study specific procedure.
- Healthy participants as established by medical history and clinical examination before entering into the study.
- A male or female of Chinese origin, between and including, 6 and 10 weeks (42-76 days) of age at the time of study enrolment.
- Born after a gestation period of 36 to 42 weeks inclusive.

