5.5. Criteria for temporarily delaying enrolment and/or study intervention administration

Enrolment/study intervention administration may be postponed within the permitted time interval until transient conditions cited below are resolved:

- Non-rotavirus GE within 7 days preceding the study intervention administration.
- Acute disease and/or fever at the time of enrolment and/or study intervention administration. Refer to the SoA (Section 1.3) for fever definition and preferred location for measuring temperature in this study.
- Participants with a minor illness (such as mild diarrhea, mild upper respiratory infection) without fever may be enrolled and/or vaccinated at the discretion of the investigator.
- Participants with known COVID-19 positive contacts within the past 14 days.

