8. STUDY ASSESSMENTS AND PROCEDURES

Protocol waivers or exemptions are only permitted when necessary for the management of immediate safety concerns for the participant.

Immediate safety concerns should be discussed with the sponsor as soon as they occur or when the study team becomes aware of them. The purpose of this communication is to determine if the participant(s) should discontinue the study intervention.

Study procedures and their timing are summarized in the SoA (Section [1.3](#)). Adherence to the study design requirements, including those specified in the SoA, is essential and required for study conduct.

All screening evaluations must be completed, and the results reviewed before confirming that potential participants meet all eligibility criteria.

The investigator will maintain a log of all participants screened. All relevant information, such as confirmation of eligibility and reasons for screening failure will be mentioned in this screening log.

Procedures conducted as part of routine clinical management (e.g., hematologic profiles), and obtained before the participant's parent(s)/LAR(s) signed the Informed Consent Form (ICF), may be used for screening and/or for establishing a clinical baseline (provided the procedure met protocol specified criteria and was performed within the time frame defined in the SoA [Section [1.3](#)]).

The Pharmacy Manual provides the investigator and site personnel with detailed administrative and technical information that does not impact participant safety.

During special circumstances (e.g., COVID-19 pandemic), the specific guidance from local public health and other competent authorities regarding the protection of individuals' welfare must be applied. For the duration of such special circumstances, the following measures may be implemented for enrolled participants:

- Biological samples may be collected at a different location* other than the study site or at participant's home. Biological samples should not be collected if they cannot be processed in a timely manner or appropriately stored until the intended use.
- If despite best efforts it is not possible to collect the biological samples within the interval predefined in the protocol, then the interval may be extended up to a maximum length of 60 days (see [Table 3](#) and [Table 4](#)).

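### The special-circumstances Visit 1-to-Visit 2 allowance of 14-45 days carries no first-dose age limit, so Section 4.2's assurance on age at first dose holds for scheduled dosing but not for that allowance

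*Protocol*

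**What the plan says.** Protocol Section 4.2 justifies the enrolment age by what it secures at first dose: "This will ensure compliance with the recommendations mentioned below, including for participants of the Co-administration group who will receive the first dose of". The timing assumed in that sentence, for Rotarix "and IPV at 2 weeks after enrolment", matters below. Two of the recommendations listed there set an upper age for a first dose. The CDC item says that first Rotarix "should be given before an infant is 15 weeks of age and the second dose before they turn 8 months old". The China item puts IPV at "no later than 13 weeks of age for the first dose". The EU item gives no upper age for the first Rotarix dose; it requires the course to be complete by 24 weeks.

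Age is restricted at entry only. Section 5.1 admits infants between "6 and 10 weeks (42-76 days) of age at the time of study enrolment". After that, intervals govern. For Visit 1 to Visit 2 the ordinary window in Table 3 is "14-18 days between study enrolment and Dose 1 of IPV" and Rotarix. In special circumstances Tables 3 and 4 widen it to 14-45 days, and SAP Tables 4 and 5 repeat this. Visit 2 is where Co-administration infants receive both first doses and Staggered infants receive first IPV. Staggered infants receive first Rotarix at Visit 1.

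Section 5.5 says: "Enrolment/study intervention administration may be postponed within the permitted time interval until transient conditions cited below are resolved". Section 8, on special circumstances, sets one age limit: 24 weeks, for Rotarix Dose 2.

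**The concern.** The protocol states that its age rule secures compliance with named recommendations, and its own contingency rule lets a site depart from them. In special circumstances a site could follow the tables to the day and still give a first dose later than an age that Section 4.2 relies on. The sponsor did see that extended intervals need an age limit for Rotarix Dose 2, but set none for Dose 1.

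What is at stake is the accuracy of the stated safeguard and the age at which a few infants might start vaccination. It is not the primary analysis.

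**Working it through.** **Inputs.** Enrolment age 42-76 days (Section 5.1). Visit 1-to-Visit 2 interval: 15 days optimal, 14-18 allowed, 14-45 in special circumstances (Tables 3 and 4). First Rotarix before 15 weeks and first IPV no later than 13 weeks (Section 4.2). Rotarix Dose 2 limit of 24 weeks (Section 8) and Dose 1-to-Dose 2 interval of 28-36 days (Tables 3 and 4).

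**The plan's own figure.** In completed weeks, 6 × 7 = 42 and 10 × 7 + 6 = 76, which reproduces the 42-76 days in Section 5.1.

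**Recommendation ages in days.** Before 15 weeks means at most 15 × 7 − 1 = 104 days. Thirteen weeks is 13 × 7 = 91 days read strictly, or 13 × 7 + 6 = 97 days in completed weeks. The documents do not say which applies, so both are shown.

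**Latest age at Visit 2** = 76 + longest interval:

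| Timing | Latest age | Rotarix (104) | IPV (97) | IPV (91) |
|---|---|---|---|---|
| Scheduled, 15 days | 76 + 15 = 91 | met | met | met |
| Ordinary window, 18 days | 76 + 18 = 94 | met | met | 3 days over |
| Special circumstances, 45 days | 76 + 45 = 121 (17 weeks 2 days) | 17 days over | 24 days over | 30 days over |

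The Rotarix column applies to Co-administration only, because Staggered infants receive first Rotarix at no more than 76 days. The IPV columns apply to both arms.

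**Where the Rotarix age starts to be passed.** At enrolment age 76 the longest compliant interval is 104 − 76 = 28 days. At the full 45 days, the oldest compliant enrolment age is 104 − 45 = 59 days.

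**Does the Dose 2 limit close the gap indirectly?** 24 × 7 = 168 days, and 168 − 28 = 140 days is the latest Dose 1 it implies. Since 140 exceeds 121, it does not. After a first dose at 121 days, Dose 2 at the ordinary interval falls at 121 + 28 = 149 to 121 + 36 = 157 days, within 168.

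**Other provisions.** Section 5.5 bounds delay by interval. Section 7.1.1 (conditions for further doses) states no age. Section 8.2.1.4 sends sites to the product label, which is not in the documents.

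**The case against.** The strongest reply is that Section 4.2 contains no error. The sentence is tied to dosing two weeks after enrolment, and at that timing every first-dose age is met. This stands. A reader might infer that the planned schedule breaches the recommendations; the documents do not support that. The gap appears only when the special-circumstances column is used.

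Second, there are partial safeguards. Section 8 requires that "the specific guidance from local public health and other competent authorities" on participants' welfare be applied. Labels are checked at dosing visits, and the measures listed in Section 8 never mention delaying Dose 1, so the permission rests on a table column alone. This also stands, as far as it goes: guidance or labels might stop a late dose in practice, and a safety gap is not shown. But none of this text gives a site a first-dose age to apply.

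Third, the ages are recommendations. Section 4.2 also describes Rotarix as a course given between 6 and 24 weeks, and 121 days lies inside that. The plan accepts missing a softer target even on schedule: Dose 2 at 76 + 15 + 30 = 121 days passes the EU preference for before 16 weeks. This is a fair reason to keep the point minor.

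A reader might also infer that IPV needs a matching hard cap. It does not. An infant already past 13 weeks at a delayed Visit 2 has missed that recommendation whatever the site does, and refusing the study dose only delays IPV further. Applied to the whole visit, such a cap would also withhold Rotarix from Co-administration infants aged 98-104 days (92-104 on the strict reading), whom the CDC item allows.

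**Conclusion.** The point holds as a minor, optional clarification. Section 4.2's assurance is correct for scheduled dosing (at most 91 days) and does not extend to the 14-45 day allowance, which has no first-dose age limit. The worst case is a first dose at 121 days: 17 days past the CDC Rotarix age in Co-administration, and 24-30 days past the 13-week IPV age in either arm. The EU 24-week limit is still met with Dose 2 at the ordinary interval.

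This assumes that the special-circumstances column means what it says for Visit 2, and that enrolment age and delay can both be at their maxima.

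It would be tempting to gauge scale from enrolment ages: at a full 45-day delay, 76 − 60 + 1 = 17 of the 35 permitted ages could pass 104 days. Those are calendar days at maximum delay, not infants. The documents give neither the enrolment-age distribution nor the frequency of delay, so no proportion of participants can be stated. Nor do they support any claim about power or bias in the seroconversion comparison.

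**What to change.** In Section 8, beside the Dose 2 limit, and as a footnote to protocol Table 3 and SAP Table 4, state that in special circumstances the first dose of Rotarix PCV-free must be given before 15 weeks of age (at most 104 days). For an infant enrolled at 76 days this means at most 28 days after Visit 1. Say whether an infant past that age still receives IPV at the visit.

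For IPV, set no hard cap. Instruct sites to give the first dose as early as possible within the window, and limit the Section 4.2 wording on the 13-week age to scheduled timing. That also covers the 3-day excess at the end of the ordinary window on the strict reading.

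**Cost.** A protocol amendment with IEC/IRB approval (Section 10.1.1) and matching SAP text; the planned sample size is unchanged. Any Co-administration infant stopped by the limit receives no study Rotarix and leaves the PPS (SAP 6.1.3, code 1070). If no study dose is given at all, the infant also leaves the Exposed Set (code 1030). An equally delayed Staggered infant, dosed with Rotarix at Visit 1, stays in the Exposed Set. That infant may already be excluded from the PPS, because the Visit 1-to-Visit 2 row carries the PPS exclusion mark in protocol Table 4 but not in Table 3. The losses are therefore not symmetric, and the number of infants stopped by the limit should be reported by arm.

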4.3. Justification for dose

Two oral doses of *Rotarix* PCV-free will be administered at approximately 1 month interval to participants, according to the immunization schedule of *Rotarix* licensed outside of China.

Three doses of IPV will be administered in a 2, 3 and 4 months of age schedule, according to the recommended schedule for vaccination against poliovirus in China.

4.4. EoS definition

A participant is considered to have completed the study if the participant returns for the last visit or is available for the last scheduled procedure as described in the protocol.

EoS is defined as LSLV (Visit 7) or date of the last testing/reading released of the Human Biological Samples, related to primary and secondary endpoints, whichever occurs later. EoS must be achieved no later than 8 months after LSLV. EoS cannot be before LSLV.

5. STUDY POPULATION

Adherence to the inclusion and exclusion criteria specified in the protocol is essential. Deviations from these criteria are not allowed because they can jeopardize the scientific integrity, regulatory acceptability of the study or safety of the participant.

5.1. Inclusion criteria

All participants must satisfy ALL the following criteria at study entry:

- Participants' parent(s)/Legally Acceptable Representative(s) (LAR), who, in the opinion of the investigator, can and will comply with the requirements of the protocol.
- Written or witnessed/thumb printed informed consent obtained from the parent(s)/LAR(s) of the participant prior to performance of any study specific procedure.
- Healthy participants as established by medical history and clinical examination before entering into the study.
- A male or female of Chinese origin, between and including, 6 and 10 weeks (42-76 days) of age at the time of study enrolment.
- Born after a gestation period of 36 to 42 weeks inclusive.

5.2. Exclusion criteria

The following criteria should be checked at the time of study entry. The potential participant MUST NOT be included in the study if ANY exclusion criterion applies:

5.2.1. Medical conditions

- History of any reaction or hypersensitivity likely to be exacerbated by any component of the study interventions.
- Any confirmed or suspected immunosuppressive or immunodeficient condition, based on medical history and physical examination (no laboratory testing required).
- Hypersensitivity to latex.
- History of severe combined immunodeficiency.
- History of seizures or progressive neurological disease.
- Family history of congenital or hereditary immunodeficiency.
- Uncorrected congenital malformation (such as Meckel's diverticulum) of the gastrointestinal tract that would predispose for intussusception (IS).
- History of IS.
- Major congenital defects, or serious chronic illness as assessed by the investigator.
- Any contraindications to IPV.
- Previous confirmed occurrence of rotavirus gastroenteritis (RVGE).
- History of poliomyelitis.
- Participants with confirmed or suspected Coronavirus Disease 2019 (COVID-19).

5.2.2. Prior/Concomitant therapy

- Use of any investigational or non-registered product (drug, vaccine or invasive medical device) other than the study interventions during the period beginning 30 days before the first dose of study interventions (Day -29 to Day 1), or planned use during the study period.
- Planned administration/administration of a vaccine not foreseen by the study protocol in the period starting 30 days before the first dose and ending 30 days after the last dose of study interventions administration*, with the exception of the inactivated influenza vaccine, which is allowed at any time during the study and other licensed routine childhood vaccinations.
 - *In case emergency mass vaccination for an unforeseen public health threat (e.g., a pandemic) is recommended and/or organized by public health authorities outside the routine immunization program, the time period described above can be reduced if, necessary for that vaccine, provided it is used according to the local governmental recommendations and that the Sponsor is notified accordingly.
- Administration of long-acting immune-modifying drugs from birth or planned administration at any time during the study period (e.g., infliximab).
- Administration of immunoglobulins and/or any blood products or plasma derivatives from birth or planned administration during the study period.
- Chronic administration (defined as more than 14 days in total) of immunosuppressants or other immune-modifying drugs since birth. For corticosteroids, this will mean prednisone ≥ 0.5 milligram/kilogram (kg)/day, or equivalent. Inhaled, intra-articular and topical steroids are allowed.
- Previous vaccination against RV.
- Previous vaccination against poliomyelitis.

5.2.3. Prior/Concurrent clinical study experience

- Concurrently participating in another clinical study, at any time during the study period, in which the participant has been or will be exposed to an investigational or a non-investigational intervention (drug, vaccine or invasive medical device).

5.2.4. Other exclusions

- Child in care. Please refer to the [glossary of terms](#) for the definition of child in care.

5.3. Lifestyle considerations

This section is not applicable.

5.4. Screening failures

A screening failure is an individual who consents to participate in this study but is not entered in the study/randomized to a study intervention.

Limited data for screening failures (including reason for screening failure) will be collected and reported in the eCRF.

5.5. Criteria for temporarily delaying enrolment and/or study intervention administration

Enrolment/study intervention administration may be postponed within the permitted time interval until transient conditions cited below are resolved:

- Non-rotavirus GE within 7 days preceding the study intervention administration.
- Acute disease and/or fever at the time of enrolment and/or study intervention administration. Refer to the SoA (Section 1.3) for fever definition and preferred location for measuring temperature in this study.
- Participants with a minor illness (such as mild diarrhea, mild upper respiratory infection) without fever may be enrolled and/or vaccinated at the discretion of the investigator.
- Participants with known COVID-19 positive contacts within the past 14 days.

6. STUDY INTERVENTION AND CONCOMITANT THERAPY

Refer to the [Glossary of terms](#) for the definition of study intervention.

6.1. Study interventions administered

Table 7 Study interventions administered

Study intervention name:	Inactivated Poliomyelitis Vaccine Made From Sabin Strains (Vero Cells) (IPV)	Rotarix PCV-free (HRV PCV-free)
Study intervention formulation:	CC1 CC1	HRV RIX4414 CC1 Sterile water
Presentation:	CC1	CC1
Type:	Co-administered	Study
Product category:	Combination product*	Combination product*
Route of administration:	Intramuscular	Oral
Administration site:		
• Location	Refer to the Pharmacy Manual for more details	NA
• Directionality	Refer to the Pharmacy Manual for more details	NA
• Laterality	Refer to the Pharmacy Manual for more details	NA
Number of doses to be administered:	3	2
Volume to be administered by dose:	0.5 mL	1.5 mL
Packaging and labeling:	Refer to the Pharmacy Manual for more details	Refer to the Pharmacy Manual for more details
Manufacturer:	Beijing Biological Products Institute Co.,Ltd.	GSK

DAgU: D antigen unit; HRV: human rotavirus; IPV: inactivated poliovirus vaccine; mL: milliliter; NA: Not applicable; PCV: *Porcine circovirus*; PCV-free: no detection of PCV-1 and PCV-2 according to the limit of detection of the tests used

*Combining a biological product and device

Refer to Section 6.1 for schedule of study intervention administration.

Study participants must be observed closely for at least 30 minutes after the administration of the study interventions. Appropriate medical treatment must be readily available during the observation period in case of anaphylaxis, syncope.

